Period B: A 2-week double-blind, placebo-controlled treatment period consisting of Weeks 13 and 14 (the peri-operative period) in which subjects will continue the treatment on the first day of Weeks 13 and 14. The designated surgeon will measure the surface area of the actual surgery and record in source document. Surgery will occur during Week 13. The surgery and post-operative management (e.g., hospitalisation, surgical wound care) will be as per local practice.

[figure not shown]
Period C: A 10-week double-blind, placebo-controlled post-operative treatment period will occur from Week 15 through Week 24, during which the subject will continue the treatment assigned at Day 1 from Week 15 through Week 23. No study drug will be administered at Week 24, the final study visit. Subjects may begin commercial product (as prescribed by the subject's physician) after all Week 24 procedures have been completed.

Study procedures throughout the study are listed in [Appendix C](#). Safety and efficacy measurements will be performed throughout the study as described in Section 5.3.1.

The study visit window will be ± 3 days for the Week 2 and Week 4 visits and ± 7 days, relative to Baseline, for all study visits from Week 8 through Week 24. Surgery takes place at Week 13 after all Week 12 evaluations are completed. A subject will be brought back to the original visit schedule (calculated from the Baseline visit [Day 1]) if the subject is out of the visit window.

Subjects may discontinue adalimumab treatment at any time during study participation. Subjects that end study participation early will have a Premature Discontinuation Visit unless consent to participate is withdrawn.

Figure 1. Study Schematic

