5.2.3.4 Rescue Therapy

If the Study Investigator, with agreement of the designated surgeon, determines the subject must undergo excision of the HS surgical site prior to the Week 13 study visit window (i.e., more than 7 days prior to the scheduled Week 13 study visit) all study

procedures scheduled for Week 12 must be performed and recorded, and the subject must be discontinued from the study.

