5.4 Removal of Subjects from Therapy or Assessment

5.4.1 Discontinuation of Individual Subjects

A subject may withdraw from the study at any time. The Principle Investigator may discontinue any subject's participation for any reason, including an adverse event, safety concerns, or failure to comply with the protocol.

Subjects will be withdrawn from the study immediately if any one of the following occurs:

- Clinically significant abnormal laboratory result(s) or adverse event(s), as determined by the Study Investigator in consultation with the AbbVie Study Designated Physician;
 - The Study Investigator believes it is in the best interest of the subject;
 - The subject requests withdrawal from the study;
- Inclusion and exclusion criteria violation was noted after the subject started study drug, when continuation of the study drug would place the subject at risk as determined by the AbbVie Study Designated Physician (see Section 5.2 and Section 7.0);

- Introduction of prohibited medications or dosages when continuation of the study drug would place the subject at risk as determined by the AbbVie Study Designated Physician;
- Subject is non-compliant with TB prophylaxis;
- The subject develops tuberculosis, or any other significant or opportunistic infections;
- The subject becomes pregnant while on study drug;
- Subject has dysplasia of the gastrointestinal tract of a malignancy, except for localized non-melanoma skin cancer. Discontinuation for carcinoma in situ of the cervix is at the discretion of the Study Investigator;
- Subject is diagnosed with lupus-like syndrome, multiple sclerosis, or demyelinating disease;
- Subject is significantly non-compliant with study procedures that would put the subject at risk for continued participation in the trial, as determined by the Study Investigator, in consultation with the AbbVie Study Designated Physician.

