5.5 Treatments

5.5.1 Treatments Administered

All treatments administered will be assigned via Interactive Response Technology (IRT) in order to maintain blinding. During Period A (Week 0 through Week 12), all subjects will receive 4 injections initially at Day 1 (or alternatively, given as two 0.8 mL injections per day on 2 consecutive days), 2 injections at Day 15 (Week 2), and one injection weekly

from Week 4 through Week 12. During Period B, all subjects will receive one injection weekly from Week 13 through Week 14. During Period C, all subjects will receive one injection weekly from Week 15 through Week 23. No study drug will be administered at the Week 24 or Premature Discontinuation Visit.

Study drug will be provided as a sterile, preservative-free solution for subcutaneous (SC) administration in 1 mL pre-filled syringes containing adalimumab 40 mg/0.8 mL or placebo (0.8 mL). The subject should be instructed to store the pre-filled syringe in the outer carton (in order to protect from light) in the refrigerator at 2° to 8°C/36° to 46°F, and that syringes should not be stored in a freezer.

Study drug will be administered SC using sterile technique by the subject or designee (e.g., family member, friend, health care professional) at the study site, or at home via self-injection following proper training ([Appendix P](#)) or by a qualified designee. At each Study visit qualified research personnel will observe the subject or designee during the injection to ensure proper technique. The subject should place the used syringe in the sharps disposal container, which will be provided to the subject at each study visit (unless prohibited by local regulations) or less frequently depending upon the size of the container.

Period A

Subjects randomised to Arm 1 will receive:

- 160 mg/3.2 mL adalimumab at the Baseline Study visit (Day 1) administered as four 40 mg injections SC (or two 0.8 mL injections on two consecutive days, i.e., Day 1 and Day 2)
- 80 mg/1.6 mL adalimumab at the Week 2 (Day 15) Study visit administered as two 40 mg injections SC
- 40 mg/0.8 mL adalimumab every week (ew) from Week 4 (Day 29) through Week 12 administered (either at the Study visit or at home as appropriate) as one 40 mg injection SC

Subjects randomised to Arm 2 will receive:

- 3.2 mL placebo at the Baseline Study visit (Day 1) administered as four 40 mg injections SC (or two 0.8 mL injections on two consecutive days, i.e., Day 1 and Day 2)

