6.1.1 Definitions

6.1.1.1 Adverse Event

An adverse event (AE) is defined as any untoward medical occurrence in a patient or clinical investigation subject administered a pharmaceutical product and which does not necessarily have a causal relationship with this treatment. An AE can therefore be any unfavorable and unintended sign (including an abnormal laboratory finding), symptom, or disease temporally associated with the use of a medicinal product, whether or not the event is considered causally related to the use of the product.

Such an event can result from use of the drug as stipulated in the protocol or labeling, as well as from accidental or intentional overdose, drug abuse, or drug withdrawal. Any worsening of a pre-existing condition or illness is considered an AE. Worsening in severity of a reported adverse event should be reported as a new AE. Laboratory abnormalities and changes in vital signs are considered to be AEs only if the event results in discontinuation from the study, necessitates therapeutic medical intervention, meets protocol specific criteria (see Section 6.1.7 regarding toxicity management) and/or if the Study Investigator considers the event to be an AE.

An elective surgery or procedure scheduled to occur during a study will not be considered an AE if the surgery or procedure is being performed for a pre-existing condition and the surgery/ or procedure has been pre planned prior to study entry. However, if the pre-existing condition deteriorates unexpectedly during the study (e.g., surgery performed

earlier than planned), then the deterioration of the condition for which the elective surgery/procedure is being done will be considered an AE.

In order to be eligible for this study a subject must require surgery due to HS and the surgery date will be determined after enrollment. The need for rescue surgery of the designated HS surgical site (i.e., surgery prior to Week 13) will not be recorded as an AE; rather the reason for surgery will be recorded on the appropriate eCRF as described in Section 5.3.2.4 and the subject will be withdrawn from the study.

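### Protocol 6.1.1.1 requires withdrawal for early rescue surgery without the 7-day window of the dedicated rule in 5.2.3.4, and points the reader to the assay section

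*Protocol*

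**What the plan says.** Two places in the protocol deal with early excision of the designated surgical site.

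- **Section 5.2.3.4 (Rescue Therapy)** is the dedicated rule. It applies when the investigator, with the surgeon's agreement, decides that excision must take place "prior to the Week 13 study visit window (i.e., more than 7 days prior to the scheduled Week 13 study visit"). The Week 12 procedures are then carried out and the subject is discontinued.
- **Section 6.1.1.1 (Adverse Event)** says: "The need for rescue surgery of the designated HS surgical site (i.e., surgery prior to Week 13) will not be recorded as an AE". The reason for surgery is instead to be entered on the eCRF "as described in Section 5.3.2.4 and the subject will be withdrawn from the study".

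The list in Section 5.4.1 that opens "Subjects will be withdrawn from the study immediately if any one of the following occurs" has no item for early surgery. Section 5.3.2.4, which 6.1.1.1 cites, covers the adalimumab and anti-adalimumab antibody assays and does not mention surgery.

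The calendar comes from three statements. Section 5.5.1 gives "40 mg/0.8 mL adalimumab every week (ew) from Week 4 (Day 29) through Week 12 administered". For Period B, Section 5.1.1 describes a period "in which subjects will continue the treatment on the first day of Weeks 13 and 14". Section 5.1.1 also sets a visit window of plus or minus 7 days, "relative to Baseline, for all study visits from Week 8 through Week 24", and adds: "Surgery takes place at Week 13 after all Week 12 evaluations are completed".

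**The concern.** Both passages end in removal from the study, but only one has a window. The parenthesis in 6.1.1.1 opens with *i.e.*, so it reads as a definition of rescue surgery, and the stated consequence is withdrawal. The withdrawal list in 5.4.1 does not say which cut-off governs, and the cross-reference in 6.1.1.1 leads away from the section that contains the window.

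The days at issue are plausible surgery days. The Week 12 visit is scheduled for Day 85 and may fall up to 7 days earlier, and surgery may follow once its evaluations are complete. A site that withdraws such a subject under 6.1.1.1 gives up post-operative follow-up that 5.2.3.4 does not ask it to give up. A site that keeps the subject could be queried, because Section 7.0 counts failure to withdraw a subject who meets withdrawal criteria as a reportable deviation.

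**Working it through.** **Calendar.** Baseline is Day 1, and Section 5.5.1 fixes Week 2 as Day 15 and Week 4 as Day 29. The formula Day = 7 × week + 1 reproduces all three: 7 × 0 + 1 = 1, 7 × 2 + 1 = 15, 7 × 4 + 1 = 29. It then gives:

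- Week 12: 7 × 12 + 1 = Day 85, the last weekly dose of Period A.
- Week 13: 7 × 13 + 1 = Day 92, the first dose of Period B.

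Day 92 is derived; the protocol does not state it. The scheduled Week 13 visit is assumed to fall on the first day of Week 13.

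**The two rules.** Let d be the day of surgery and W = 92.

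- 5.2.3.4: W − d > 7, so d ≤ W − 8 = 84.
- 6.1.1.1, read literally: d < W, so d ≤ W − 1 = 91.
- Difference: Days W − 7 to W − 1, that is Days 85 to 91, or 7 days. Day 85 belongs to the range because it is exactly 7 days before Day 92, not more than 7.

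**Other readings of Week 13.**

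| Reading | 5.2.3.4 applies up to | 6.1.1.1 applies up to | Days that differ |
|---|---|---|---|
| Week 13 and its visit both start on Day 92 | Day 84 | Day 91 | 85–91 (7 days) |
| Week 13 and its visit both start on Day 85 | Day 77 | Day 84 | 78–84 (7 days) |
| Visit on Day 92, but Week 13 taken to begin on Day 85 | Day 84 | Day 84 | none |

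The third reading needs Week 13 to begin on the day of the Week 12 dose, which the dosing text does not support.

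**Consequence for one subject.** Take a subject operated on in Days 85 to 91 after an on-time Week 12 visit and withdrawn only because of 6.1.1.1.

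- Primary endpoint and ranked 1: the Week 12 lesion counts are already recorded, so nothing changes.
- Ranked 2 (HiSCR-es at Week 24): the assessment is missing and non-responder imputation applies. The SAP 4.7 exception needs a response both before and after the missed visit, and no study visit follows Week 24. With 100 subjects per arm the arm's rate falls by at most 1/100 = 1.0 percentage point. The fall is zero if the subject would not have responded anyway.
- Ranked 3 and 4: SAP 4.7 forces no change in planned area and no less extensive surgery for subjects who discontinued before surgery for listed reasons. The last of these is planned surgery performed before Week 13. If the condition of discontinuing before surgery governs the whole list, a subject who has been operated on does not clearly meet it. If the last item stands alone, the forcing depends on the date of surgery and 6.1.1.1 adds nothing. If it means discontinued because of early surgery, the forcing follows from the withdrawal. The text does not settle which is meant.

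The documents give no rate of surgery on Days 85 to 91, so no loss of power can be computed.

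**The case against.** The best reply is that 6.1.1.1 is shorthand. It sits among the adverse event definitions, its purpose is to say that rescue surgery is not an adverse event, and its subject is rescue surgery of one designated site, not any operation. Planned surgery done a few days early is not obviously rescue. A specific rule in its own section normally prevails over a passing gloss. If the general window is applied, Week 13 runs from Day 85 to Day 99 and surgery before it ends at Day 84, which agrees with 5.2.3.4.

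This harmonised reading is reasonable, and it shows that 6.1.1.1 is the outlier. It does not make 6.1.1.1 correct: the sentence states a consequence, and its cross-reference sends the reader to assay methods. That reference is wrong on any reading of Week 13.

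Two limits stand. Section 5.2.3.4 does not expressly keep subjects operated on in Days 85 to 91; it only does not require their discontinuation. It also does not describe how the reason for surgery is recorded, so it is the evident target of the cross-reference but does not supply everything the sentence in 6.1.1.1 refers to.

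**Conclusion.** Section 6.1.1.1 is wrong as written, and the matter is minor. Read literally, it conflicts with the dedicated rule on seven calendar days, Days 85 to 91, and it cites the wrong section. The day count rests on Week n = Day 7n + 1 and on the Week 13 visit falling on Day 92.

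The effect on the analysis is conditional. It needs surgery in that week, a site that follows 6.1.1.1 over 5.2.3.4, and a subject who would otherwise have been a Week 24 responder. Each such subject costs that arm 1.0 percentage point on ranked endpoint 2.

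A reader might infer more: that these subjects are certain to be forced to no change on ranked endpoints 3 and 4, or that the trial's efficacy conclusion is at risk. The documents do not support either. The SAP 4.7 sentence can be read in ways under which 6.1.1.1 changes nothing, the primary and first ranked endpoints rest on Week 12 data already collected, and no frequency of surgery in that week is given.

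**What to change.** In Protocol 6.1.1.1, replace the parenthesis that defines rescue surgery with: *(i.e., excision more than 7 days prior to the scheduled Week 13 study visit, as defined in Section 5.2.3.4)*. Change the cross-reference from 5.3.2.4 to 5.2.3.4. Both rules then apply up to Day 84 and differ on no day.

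In SAP 4.7, use the same cut-off for the item on planned surgery before Week 13. Surgery inside the allowed window is then analysed with its actual area and type and is not forced to no change.

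The cost is one phrase and one section number in the protocol, and one phrase in the SAP. Design, sample size, endpoints and analysis methods stay as they are.

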6.1.1.2 Serious Adverse Events

If an adverse event meets any of the following criteria, it is to be reported to AbbVie as a serious adverse event (SAE) within 24 hours of the study site being made aware of the SAE.

Death of Subject	An event that results in the death of a subject.
Life-Threatening	An event that, in the opinion of the investigator, would have resulted in immediate fatality if medical intervention had not been taken. This does not include an event that would have been fatal if it had occurred in a more severe form.
Hospitalization or Prolongation of Hospitalization	An event that results in an admission to the hospital for any length of time or prolongs the subject's hospital stay. This does not include an emergency room visit or admission to an outpatient facility.
Congenital Anomaly	An anomaly detected at or after birth, or any anomaly that results in fetal loss.
Persistent or Significant Disability/Incapacity	An event that results in a condition that substantially interferes with the activities of daily living of a study subject. Disability is not intended to include experiences of relatively minor medical significance such as headache, nausea, vomiting, diarrhea, influenza, and accidental trauma (e.g., sprained ankle).

Important Medical Event Requiring Medical or Surgical Intervention to Prevent Serious Outcome

An important medical event that may not be immediately life-threatening or result in death or hospitalization, but based on medical judgment may jeopardize the subject and may require medical or surgical intervention to prevent any of the outcomes listed above (i.e., death of subject, life-threatening, hospitalization, prolongation of hospitalization, congenital anomaly, or persistent or significant disability/incapacity). Additionally, any elective or spontaneous abortion or stillbirth is considered an important medical event. Examples of such events include allergic bronchospasm requiring intensive treatment in an emergency room or at home, blood dyscrasias or convulsions that do not result in inpatient hospitalization, or the development of drug dependency or drug abuse.

For SAEs with the outcome of death, the date and cause of death will be recorded on the appropriate case report form.

6.1.1.3 Adverse Events of Special Interest

Adverse events of special interest as defined in [Table 3](#), and adverse events concerning the surgical site will be collected and analysed.

Table 3. Adverse Events of Special Interest

Serious and nonserious opportunistic infections, including the following bacterial, fungal, viral and parasitic infections: Aspergillus, Blastomyces, Candida, Coccidioides, Cryptococcal, Cytomegalovirus, Histoplasma, Listeria, Nocardia, Paracoccidioides, Pneumocystis, Toxoplasma, Tuberculosis, Herpes, Bacillary angiomatosis, Mucormycosis, Progressive Vaccinia, Zygomycosis, BK virus, and JC virus
Lymphoma
Hepatosplenic T-cell lymphoma
Leukemia
Non-melanoma skin cancer (NMSC)
Other malignancies (except lymphoma, leukemia and NMSC)
Immune reactions including lupus, lupus-like reactions, and severe allergic reactions
Congestive heart failure (CHF)
Cerebrovascular accident (CVA)
Myocardial infarction (MI)
CNS demyelinating disorders (including MS and Guillain-Barré syndrome)
Hepatic events that are serious or lead to permanent discontinuation of study drug (e.g., persistent liver function test abnormalities, acute liver failure and other serious hepatic events)
Hematologic events that are serious or lead to permanent discontinuation of study drug (e.g., aplastic anemia, granulocytopenia, Granulocyte Maturation Arrest, leukopenia, neutropenia, nancytopenia and thrombocytopenia)
Worsening of Psoriasis
Vasculitis
Diverticulitis
Intestinal perforation

6.1.2 Adverse Event Severity

The investigator will use the following definitions to rate the severity of each adverse event:

Mild	The adverse event is transient and easily tolerated by the subject.
Moderate	The adverse event causes the subject discomfort and interrupts the subject's usual activities.

Severe The adverse event causes considerable interference with the subject's usual activities and may be incapacitating or life-threatening.

6.1.3 Relationship to Study Drug

The investigator will use the following definitions to assess the relationship of the adverse event to the use of study drug:

Reasonable Possibility An adverse event where there is evidence to suggest a causal relationship between the study drug and the adverse event.

No Reasonable Possibility An adverse event where there is no evidence to suggest a causal relationship between the study drug and the adverse event.

For causality assessments, events assessed as having a reasonable possibility of being related to the study drug will be considered "associated." Events assessed as having no reasonable possibility of being related to study drug will be considered "not associated." In addition, when the investigator has not reported a causality or deemed it not assessable, AbbVie will consider the event associated.

If an investigator's opinion of no reasonable possibility of being related to study drug is given, an Other cause of event must be provided by the investigator for the serious adverse event.

[figure not shown]
6.1.4 Adverse Event Collection Period

All AEs reported from the time of study drug administration until either the final follow-up telephone call (approximately 70 days following discontinuation of study drug administration) or the date at which the subject initiated commercial adalimumab will be collected, whether solicited or spontaneously reported by the subject. In addition, SAEs and protocol-related nonserious AEs will be collected from the time the subject signed the study-specific informed consent. Adverse event information will be collected and recorded on the appropriate eCRFs.

Subjects will be contacted approximately 70 days following study drug discontinuation for an assessment of any new or ongoing AEs/AESI/SAEs as discussed in Section 5.3.1.1.

Adverse event information will be collected as shown in Figure 2.

Figure 2. Adverse Event Collection

6.1.5 Adverse Event Reporting

In the event of an SAE, and additionally, any nonserious event of malignancy in subjects 30 years of age and younger, whether related with study drug or not, the Study Investigator will notify AbbVie Clinical Pharmacovigilance within 24 hours of the study site being made aware of the serious adverse event by entering the SAE or nonserious event of malignancy in subjects 30 years of age or younger data into the electronic data capture (EDC) system. All SAEs and nonserious events of malignancy in subjects 30 years of age and younger that occur prior to the study site having access to the RAVE[®] system or if RAVE[®] is not operable, should be documented on the SAE Non-CRF forms and emailed (preferred route) or faxed to AbbVie Clinical Pharmacovigilance within 24 hours of the study site being made aware of the serious adverse event.

Email: [REDACTED]

FAX to: [REDACTED]

For safety concerns, contact the Immunology Safety Team at:

[REDACTED]
AbbVie
[REDACTED]
[name]
[name]

Telephone Contact Information:

[REDACTED]
Email: [REDACTED]

For any subject safety concerns, please contact the physician listed below:

Study Designated Physician:

[REDACTED]
[name]
[name]

Telephone Contact Information:

Office: [REDACTED]
Mobile: [REDACTED]
Email: [REDACTED]

In emergency situations involving study subjects when the Study Designated Physician is not available by telephone, please contact the 24-hour AbbVie Medical Escalation Hotline where your call will be re-directed to a designated backup AbbVie physician:

Telephone: [REDACTED]

The sponsor will be responsible for Suspected Unexpected Serious Adverse Reactions (SUSAR) reporting for the Investigational Medicinal Product (IMP) in accordance with Directive 2001/20/EC. For AbbVie IMPs used in Phase 4 studies or for non-AbbVie

IMP, also include: The reference document used for SUSAR reporting in the EU countries will be the most current version of the SmPC.

